4.1 Study objectives

The purpose of this study is to evaluate the long-term safety and performance of the ARGOS-SC suprachoroidal pressure sensor in patients with glaucoma who underwent non-penetrating glaucoma surgery.

4.1.1 Primary objectives

Performance:

To evaluate the limits of agreement between measurements with the GAT, DCT and the ARGOS-SC system from month 12 throughout month 36 following implantation.

4.1.2 Secondary objectives

Safety:

To evaluate the safety and tolerability of the ARGOS-SC pressure sensor throughout a follow-up period from V09 (month 12) throughout V13 (month 36).

Performance:

To evaluate the performance of the ARGOS-SC system from V09 (month 12) throughout V13 (month 36).

4.2 Study endpoints

4.2.1 Primary endpoint

Performance:

Level of agreement between measurements made using GAT, Pascal DCT and the ARGOS-SC system from V09 (month 12) throughout V13 (month 36).

4.2.2 Secondary endpoints

Safety:

Number of patients experiencing a device-related SAE (SADE) at any time from V09 (month 12) throughout V13 (month 36).

Incidence, nature, severity and seriousness of observed adverse events and adverse device events at any time from V09 (month 12) throughout V13 (month 36).

Performance:

Incidence, nature and seriousness of observed device malfunctions during from V09 (month 12) throughout V13 (month 36).

Repeatability of ARGOS-SC measurement

Utility

User acceptance of the ARGOS-SC system at the investigational site by means of evaluation of physician acceptance questionnaires (by investigators)

User acceptance of the ARGOS-SC system at home by means of evaluation of patient acceptance questionnaires (patients)

5 Sample Size and Power

Given by the exploratory nature of this study, the sample size is not driven by the need for a formal statistical hypothesis test with a certain degree of power. Instead, this study is driven by the desire to obtain a clinically meaningful amount of data to evaluate the long-term safety and performance of the ARGOS-SC system in patients who have been already implanted with the study device. Therefore, the maximum sample size is 24. The minimal sample size for this study is at the Sponsor's direction. This is considered to be appropriate since no experimental treatments are planned and all assessments with exception of IOP measurement using the ARGOS-SC device are established standard methods.

6 Analysis Sets

There will be only one analysis set defined in this study:

- **Full Analysis Set (FAS):**

The FAS defined according to the intention-to-treat principle will include all patients of the ARGOS-SC01 clinical investigation with an implanted ARGOS-SC pressure sensor and given their informed consent.

7 Statistical Considerations

7.1 Derived variables

The table below provides the list of derived variables applicable for this study.

Variables	Formula
Demographic and baseline characteristics	
Age [years]	Year of baseline visit – year of birth
Derivation of duration	
Study duration [days]	Date of patient's last visit or date of study discontinuation (whatever the later date is) – date of baseline visit + 1

7.2 Handling of missing data

In general, missing data will not be replaced. In tables of categorical data, missing data will be included as 'Missing' and included in the calculation of percentages.

If not otherwise specified and the calculation of periods requires the full date format dd-mm-yyyy, missing start date entries will be set to the first possible day of the month for a missing day and in case of a missing month, the first possible month of a year will be set. Missing stop date entries will be set to the last possible day of the month for a missing day and in case of a missing month, the last possible month of a year will be set.

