7.3 Methods for handling dropouts

All patients will be analysed as far as documented.

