8.1.2 Statistical outputs

8.1.2.1 Tables and graphics

Percentages will be based on the number of subjects in the analysis set.

Categorical variables will be summarized by the number of patients (n) and percentages (%). Percentages will be rounded to one decimal place.

In addition, for the primary endpoints (response rates) the 95% confidence intervals will be calculated.

Continuous variables will be summarized using descriptive statistics, including

- number of patients with non-missing data (n)
- arithmetic mean (Mean)
- 95% confidence interval of mean (if indicated)
- standard deviation (SD)
- median (Median)
- lower (25%, Q1) and upper (75%, Q3) quartile
- minimum (Min) and maximum (Max).

Analyses by visit will be performed irrespective of any time window deviations.

Some mock-up tables are presented in the appendix of this SAP.

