8.5 Primary endpoint

8.5.1 Performance

Level of agreement between measurements made using GAT, Pascal DCT and ARGOS-SC system at visit V09 - V13.

The primary outcome measures of the study eye are:

- Average of 2 – 3 measurements using GAT system at visit V09 – V13
- Average of 2 – 3 measurements using ARGOS-SC system at visit V09 – V13 roughly contemporaneous with the GAT measurements

Descriptive statistics for the GAT and ARGOS-SC measures per visit.

Descriptive statistics for the absolute difference between ARGOS-SC and GAT measures per visit.

The absolute difference between the ARGOS-SC and GAT measures will be scaled in $\leq 5\text{mmHg}$ and $> 5\text{ mmHg}$ and the frequency distribution will be displayed.

The concordance of the intraindividual measurement values of GAT and ARGOS-SC will be indicated by the concordance correlation coefficient r_{ccc} (→ see section 11.1), separate for each visit.

The Bland-Altman (mean-difference) plot and a X-Y -plot (Scatter-Plot) should illustrate the comparison of the two methods (→ see section 11.2).

The level of agreement between Pascal DCT and ARGOS-SC will be evaluated analogously.

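### As written, the SAP calculates the per-visit 5 mmHg agreement percentages on the whole FAS, so missing pairs lower them; this is not reconciled with the protocol

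*SAP*

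**What the plan says.** Two SAP rules set the percentage base. Section 7.2: "In tables of categorical data, missing data will be included as 'Missing' and included in the calculation of percentages". Section 8.1.2.1: "Percentages will be based on the number of subjects in the analysis set". Section 6 defines a single set, the FAS, consisting of "all patients of the ARGOS-SC01 clinical investigation with an implanted ARGOS-SC pressure sensor and given their informed consent".

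Section 8.5.1 classifies the absolute ARGOS-SC/GAT difference as up to 5 mmHg or above 5 mmHg and asks for the frequency distribution. The mock-up of Table 2.1.1 shows this by visit, V09 to V13. For the second comparator: "The level of agreement between Pascal DCT and ARGOS-SC will be evaluated analogously". Section 7.4 describes all primary and secondary outcome measures as categorical, which brings this distribution under the 7.2 rule.

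Four other places bear on the base:

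- SAP 7.3, on drop-outs: "All patients will be analysed as far as documented".
- Protocol 9.8: analyses use observed cases, and missing values are not replaced.
- Protocol 9.1.4: the 65% agreement target refers to measurement pairs.
- SAP section 9: two changes from the protocol are listed (self-measurements not recorded, interim analyses not performed). Neither concerns missing data or denominators.

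**The concern.** A patient who misses a visit, has dropped out, has no DCT value or has no sensor reading gives no pair. On the FAS base that patient counts in the denominator and cannot count as agreeing. The percentage then mixes two quantities: how well the methods agree, and how many patients were measured with both.

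Missing pairs are foreseeable. Follow-up lasts two years, drop-outs are not replaced (protocol 8.3.2.2), DCT is done only where available (protocol 8.3.12.13), and a non-functional implant may stay in the eye (protocol 8.3.13.1), so a patient can attend without giving a pair. The table runs from month 12 to month 36 in a study of long-term performance. Growing attrition could therefore look like agreement declining over time.

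The rule also puts two bases in one table. Under SAP 8.1.2.1 the mean difference is calculated on patients with non-missing data, while the agreement rows beneath it are calculated on the FAS. The same section says that "for the primary endpoints (response rates) the 95% confidence intervals will be calculated". It does not say which rates are meant; if this one is, its interval takes the same base.

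**Working it through.** The plan gives no figure that rests on this rule, so there is nothing to reproduce. The documents supply the maximum sample size of 24 (protocol 8.3.6, SAP 5) and the 5 mmHg cut (SAP 8.5.1). They give no attendance, drop-out rate or DCT availability. Those inputs are assumed below, with an FAS of 24. Confidence intervals are exact (Clopper-Pearson), also an assumption, because the SAP names no method.

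**Formula.** Let x be the number of pairs within 5 mmHg and n the number of observed pairs at a visit.

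- Observed pairs: x / n
- SAP as written: x / 24 = (x / n) × (n / 24)

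**GAT with assumed attrition and stable agreement**

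| | V09 | V10 | V11 | V12 | V13 |
|---|---|---|---|---|---|
| Pairs observed, n | 24 | 22 | 21 | 20 | 18 |
| Within 5 mmHg, x | 19 | 18 | 17 | 16 | 14 |
| x / n | 79.2% | 81.8% | 81.0% | 80.0% | 77.8% |
| x / 24 (as written) | 79.2% | 75.0% | 70.8% | 66.7% | 58.3% |
| Above 5 mmHg, (n − x) / 24 | 20.8% | 16.7% | 16.7% | 16.7% | 16.7% |
| Missing, (24 − n) / 24 | 0% | 8.3% | 12.5% | 16.7% | 25.0% |

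Agreement among observed pairs stays between 77.8% and 81.8%, while the displayed figure falls by 20.9 percentage points (79.2 − 58.3). At V13 the 95% interval is 52.4 to 93.6% for 14/18 and 36.6 to 77.9% for 14/24.

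**Sensitivity to the number missing**, with true agreement of 80%: 80% × (24 − m) / 24 gives 80.0% for m = 0, 73.3% for m = 2, 66.7% for m = 4 and 60.0% for m = 6.

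**DCT.** With a DCT pair in k of 24 patients, the largest percentage that can be shown is k / 24: 75% for k = 18, 50% for k = 12, 25% for k = 6. With 12 of 12 pairs agreeing, the observed rate is 100% (73.5 to 100) and the rate as written is 12/24 = 50% (29.1 to 70.9). No drop-out is needed for this; site equipment alone sets the ceiling.

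**Passages side by side.** SAP 7.2 and 8.1.2.1 lead to the same denominator and contain no exception. Protocol 9.1.4 counts pairs, and a missed visit contributes none. Protocol 9.8 confines analyses to observed cases. The SAP does not reconcile these, and section 9 is silent on the point.

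**The case against.** The strongest point is the layout of mock-up Table 2.1.1. The agreement block has its own per-visit n, which the SAP abbreviations define as patients with non-missing data, and it has only the two difference rows, with no 'Missing' row. A programmer could reasonably use observed pairs. This stands as evidence that the programmed denominator is uncertain. It does not override the text: the mock-ups are labelled as examples, Table 1.2 has the same generic layout, and at most the SAP then disagrees with itself.

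Second, restricting analyses to observed cases mainly rules out imputation. It does not forbid a 'Missing' row, and protocol 9.8 names no percentage base. That is fair. The tension lies in the base: dividing by the FAS treats an absent pair as one that did not agree, which does not fit a target expressed in measurement pairs.

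Third, SAP 7.3 and the drop-out wording of protocol 9.8 can be read as not carrying drop-outs into later visits, and nothing says that DCT not done for lack of equipment counts as missing. Both readings are possible, but neither is stated.

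Fourth, the consequence is limited. All SAP analyses are descriptive, and the 65% target applies to pairs rather than to each visit, so no pass or fail result turns on this percentage. The share above 5 mmHg does not rise, and a displayed 'Missing' row would let a reader recover the observed rate. The FAS base follows the stated intention-to-treat principle and does not flatter the device. All of this is accepted; it limits the weight of the point without removing it.

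**Conclusion.** The concern holds for the SAP as written. The per-visit agreement percentages for GAT and DCT would be diluted by exactly the share of the FAS without a pair, and this is neither reconciled with protocol 9.8 and 9.1.4 nor declared as a change. It should be fixed before the tables are programmed, because two competent programmers could report different primary-endpoint percentages from the same data.

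The size depends on attendance and DCT availability, which the documents do not give. It is zero with complete data. Under the assumptions above it reaches about 20 percentage points for GAT at V13 with 6 of 24 pairs missing, and 50 points for DCT if half the patients have it. The mean differences, concordance coefficient and plots are not affected. Confidence is high about what the text says, and lower about what would actually be programmed.

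**What to change.** Add one sentence to each of SAP 7.2 and 8.1.2.1 exempting the paired IOP agreement tables (GAT and DCT), and any confidence intervals for these rates, from the FAS base. The denominator should be patients with both a comparator value and an ARGOS-SC value at that visit.

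In Tables 2.1.1 and 2.1.2, show the number of FAS patients without a pair as a count outside the percentages. Where the CRF allows, count separately those with a comparator value but no sensor value. SAP 8.6.2 and 8.8.2 already tabulate device malfunctions and deficiencies, but this row keeps sensor failures visible next to the rate from which they drop out. State in 8.1.2.1 which rates the confidence intervals cover.

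If the sponsor prefers the FAS base, declare and justify it in SAP section 9 and show the 'Missing' row in both tables.

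The cost is two sentences and one or two count rows per table, with no new measurement.

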7.3 Methods for handling dropouts

All patients will be analysed as far as documented.

7.4 Handling of outliers

Since all primary and secondary outcome measures and most of the other variables are based on categorical variables, there is no need regarding a specific handling of outliers.

8 Statistical Methods

8.1 General statistical conventions

8.1.1 Statistical analyses in SAS

All analyses will be conducted descriptively. The tables, graphics and statistical analyses will be performed using the statistical software SAS® 9.4 (TS1M6; or later) for Microsoft Windows.

8.1.2 Statistical outputs

8.1.2.1 Tables and graphics

Percentages will be based on the number of subjects in the analysis set.

Categorical variables will be summarized by the number of patients (n) and percentages (%). Percentages will be rounded to one decimal place.

In addition, for the primary endpoints (response rates) the 95% confidence intervals will be calculated.

Continuous variables will be summarized using descriptive statistics, including

- number of patients with non-missing data (n)
- arithmetic mean (Mean)
- 95% confidence interval of mean (if indicated)
- standard deviation (SD)
- median (Median)
- lower (25%, Q1) and upper (75%, Q3) quartile
- minimum (Min) and maximum (Max).

Analyses by visit will be performed irrespective of any time window deviations.

Some mock-up tables are presented in the appendix of this SAP.

8.1.2.2 Patient data listings

Disposition of patient, concomitant medication, adverse events, device deficiencies, abnormal findings of ophthalmic examination will be presented in individual patient data listings. All listings will be sorted by patient ID and visit (if applicable). Unless otherwise stated, data listings will be based on the FAS.

One mock-up listing is presented in the appendix of this SAP.

8.1.3 Level of significance

All analyses will be conducted descriptively, so that no statistical tests will be performed. All confidence intervals which will be calculated will be two-sided 95% confidence intervals.

8.1.4 Subgroup analyses

The performance of subgroup analyses will be decided at a final data review meeting preceding the statistical analysis, based on the actual distribution of subjects.

8.1.5 Interim analyses

Interim analyses are not planned.

8.2 Disposition of patients

The number and percentage of those who complete the follow-up study will be tabulated. The number and percentage of early withdrawals will also be tabulated, along with the reason for the drop-out. Patient disposition will be listed.

8.3 Demographic and other baseline characteristics

Demographic characteristics (age, sex, educational level), lens status, anti-glaucoma medication, and other previous and concurrent treatments will be tabulated.

Specifications of specific medication will be listed only.

8.4 Treatment

Not applicable

8.5 Primary endpoint

8.5.1 Performance

Level of agreement between measurements made using GAT, Pascal DCT and ARGOS-SC system at visit V09 - V13.

The primary outcome measures of the study eye are:

- Average of 2 – 3 measurements using GAT system at visit V09 – V13
- Average of 2 – 3 measurements using ARGOS-SC system at visit V09 – V13 roughly contemporaneous with the GAT measurements

Descriptive statistics for the GAT and ARGOS-SC measures per visit.

Descriptive statistics for the absolute difference between ARGOS-SC and GAT measures per visit.

The absolute difference between the ARGOS-SC and GAT measures will be scaled in $\leq 5\text{mmHg}$ and $> 5\text{ mmHg}$ and the frequency distribution will be displayed.

The concordance of the intraindividual measurement values of GAT and ARGOS-SC will be indicated by the concordance correlation coefficient r_{ccc} (→ see section 11.1), separate for each visit.

The Bland-Altman (mean-difference) plot and a X-Y -plot (Scatter-Plot) should illustrate the comparison of the two methods (→ see section 11.2).

The level of agreement between Pascal DCT and ARGOS-SC will be evaluated analogously.

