### **IOP measurement in the clinic**

IOP measurement will be conducted as a series of 2x GAT (in case of a difference of more than 2mmHg, a third GAT-measurement is required) followed by 3x ARGOS-SC system. When series of measurements are made, GAT must always be used first to avoid potential operator bias. For the ARGOS-SC measurements the patient has to stay in the same position as for the GAT-measurements (chin on chin rest, forehead installed).

Additionally (if available), a series of 2x DCT (in case of a difference of more than 2mmHg, a third DCT-measurement is required) followed by 3x ARGOS-SC will be performed after the series of GAT and ARGOS-SC measurements. For the ARGOS-SC measurements, the patient has to stay in the same position as for the DCT-measurements (chin on chin rest, forehead installed).

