### **ARGOS-SC system measurement by the subject at home**

Subjects will receive detailed instruction in the use of the MESOGRAPH reading device. Subjects will be requested to perform at least 4 IOP measurements daily with the MESOGRAPH, one each in the morning after getting up, at noon, in the afternoon and in the evening before going to bed.

No data will be recorded manually by the subject. The MESOGRAPH reading device, which is capable of storing up to 3,000 measurements, will be connected to an external GSM module, which will transfer the measured value directly to a secure database. Investigators can log into the database in order to track the pressure levels of their patients as required.

The MESOGRAPH will also be brought to every visit, at which time site staff will assess its functionality and delete recorded IOP data from its memory.

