#### **9.1.4 Performance Analysis**

The probability distribution of the difference of the paired measurements grouped within 1 mmHg will be compared to the primary objective of the accepted 65% of the measurements to agree between +/- 5 mmHg for > 60 measurement pairs.

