8.6.2 Performance

- Incidence, nature and seriousness of observed device malfunctions from V09 (month 12) throughout V13 (month 36). This parameter will be analysed using a frequency table.
- The variables
 - Standard deviation of 2 – 3 measurements using GAT system
 - Standard deviation of 2 – 3 measurements using ARGOS-SC system at visit V09 – V13 will be analysed descriptively per visit and overall.

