11.2 Bland-Altman Plot

Bland and Altman introduced the Bland-Altman plot to describe agreement between two quantitative measurements by constructing limits of agreement. These statistical limits are calculated by using the mean and the standard deviation (s) of the differences between two measurements. To check the assumptions of normality of differences and other characteristics, they used a graphical approach.

The resulting graph is a scatter plot XY, in which the Y axis shows the difference between the two paired measurements (x-y) and the X axis represents the average of these measures $((x+y)/2)$. In other words, the difference of the two paired measurements is plotted against the mean of the two measurements. Bland-Altman recommended that 95% of the data points should lie within $\pm 2s$ of the mean difference. This is the most common way to plot the Bland-Altman method.

The bias is computed as the value determined by one method minus the value determined by the other method. If one method is sometimes higher, and sometimes the other method is higher, the average of the differences will be close to zero. If it is not close to zero, this indicates that the two assay methods are systematically producing different results.

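### The limits of agreement describe averages of 2–3 readings and are too narrow for a single ARGOS-SC reading; add a single-reading row and label the existing limits

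*SAP*

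**What the plan says.** SAP 8.5.1 defines two primary outcome measures for the study eye: "Average of 2 – 3 measurements using GAT system at visit V09 – V13" and "Average of 2 – 3 measurements using ARGOS-SC system at visit V09 – V13 roughly contemporaneous with the GAT measurements". The per-visit differences, the split at 5 mmHg, the concordance correlation and the Bland-Altman plots are specified from these measures, and DCT is to be evaluated analogously.

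On the limits, SAP 11.2 states: "These statistical limits are calculated by using the mean and the standard deviation (s) of the differences between two measurements". It contains no replicate term, and the lists of tables and figures in SAP 11.3 show no agreement analysis of single readings.

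Within-series variation is planned as a separate repeatability output in SAP 8.6.2 ("Standard deviation of 2 – 3 measurements using ARGOS-SC system at visit V09 – V13 will be analysed descriptively") and in Table 2.2.3. It is not carried into the limits.

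The protocol's clinic procedure fixes the ARGOS-SC series at three readings ("followed by 3x ARGOS-SC system"), whereas the SAP says 2–3. Home use is one reading at a time: "Subjects will be requested to perform at least 4 IOP measurements daily with the MESOGRAPH, one each in the morning after getting up", then at noon, in the afternoon and in the evening. The protocol's benchmark in section 9.1.4 is worded as the "accepted 65% of the measurements to agree between +/- 5 mmHg". SAP section 9 records that home self-measurements were not recorded.

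**The concern.** Averaging m readings removes the fraction (1 − 1/m) of the within-series variance, which is two thirds for three ARGOS-SC readings. Limits built on such averages describe how far an average of several ARGOS-SC readings may lie from an average of several GAT readings. A patient at home acts on one reading, which keeps all of that variance.

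The report could therefore quote limits and a 5 mmHg share as the agreement of ARGOS-SC measurements without saying that they apply to means. A reader could then credit one home reading with the precision of an average. Because self-measurements were not recorded, the clinic series are the only data in this analysis that can inform single-reading agreement.

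**Working it through.** The documents print no limits of agreement in patients and no within-series SD, so there is no figure of the plan's own to reproduce.

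**Inputs**
- Number of ARGOS-SC readings per series: m = 3 (protocol, IOP measurement in the clinic). The SAP's 2–3 would also allow m = 2.
- SD of the difference of averages, s_avg: not in the text. Assumed 3.0 mmHg, then varied.
- ARGOS-SC within-series SD, σ_A: not in the text. Assumed 0.5–1.5 mmHg.
- Nearest printed figure for σ_A: the specified 3-sigma accuracy of 2 mmHg in protocol 4.7.1.4, giving 2/3 ≈ 0.67 mmHg. This is bench accuracy, not repeatability in the eye.

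**Formulas**, assuming independent within-series errors of equal variance:
- Variance of a single ARGOS-SC reading minus mean GAT = s_avg² + (1 − 1/m)·σ_A²
- Half-width of the limits = 1.96 × SD
- Share within 5 mmHg = 2Φ(5/SD) − 1, for normal differences with zero bias

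The GAT side stays averaged because it is the clinic reference, and no GAT is taken at home.

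**Results for s_avg = 3.0, m = 3** (averages: ±5.88 mmHg, 90.4% within 5 mmHg)

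| σ_A (mmHg) | SD for one reading | Limits | Widening | Share within 5 mmHg |
|---|---|---|---|---|
| 0.5 | √(9 + 0.167) = 3.03 | ±5.93 | 0.9% | 90.1% |
| 0.67 | √(9 + 0.296) = 3.05 | ±5.98 | 1.6% | 89.9% |
| 1.0 | √(9 + 0.667) = 3.11 | ±6.09 | 3.6% | 89.2% |
| 1.5 | √(9 + 1.5) = 3.24 | ±6.35 | 8.0% | 87.7% |

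SAP 11.2 speaks of 2s rather than 1.96s. The percentage widening is the same with either multiplier.

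**Sensitivity to s_avg**, at σ_A = 1.5 and m = 3:
- s_avg = 2.5: ±4.90 becomes ±5.46 (11.4%); share 95.4% to 92.8%.
- s_avg = 4.0: ±7.84 becomes ±8.20 (4.6%); share 78.9% to 76.8%.
- s_avg = 5.35, the SD that puts exactly 65% within 5 mmHg: ±10.49 becomes ±10.76 (2.6%); share 65.0% to 63.8%.

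With m = 2, s_avg = 3.0 and σ_A = 1.5, the limits are ±6.24 (6.1%). The replicate count therefore enters the answer.

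**The case against.** The primary endpoint is in-clinic agreement between methods at the same time point, and the SAP nowhere says its limits will be applied to home readings. Section 8.5.1 states openly that the measures are averages, and 8.6.2 already plans the within-series SDs, so a reader could derive the correction. The protocol benchmark also refers to measurement pairs. Two GAT and three ARGOS-SC readings have no one-to-one pairing, and one mean pair per visit gives up to 24 × 5 = 120 pairs, which fits the protocol's requirement of more than 60. The analysis is descriptive and no test depends on it.

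All of this stands. It limits the point to the scope of the limits and how they are labelled.

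A reader might infer three stronger things that the documents do not support:

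- **That single GAT noise should also be added.** With an assumed GAT within-series SD of 1–2 mmHg and two readings, the variance becomes 9 + 0.5 + 0.167 up to 9 + 2 + 1.5. The limits would be about ±6.1 to ±6.9 (4–18% wider) and the share 89.2% to 84.3%. That describes one GAT reading against one ARGOS-SC reading. It does not describe a home reading judged against an averaged clinic reference, and most of the extra widening comes from the GAT term.
- **That the primary analysis is wrong or the 65% benchmark at risk.** The limits are correct for averages. In the main illustration the share stays far above 65%. A crossing appears only when the result already sits at the boundary.
- **That corrected limits would describe accuracy at home.** Clinic readings are directly consecutive and taken at the chin rest, so home posture and handling remain outside them.

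**Conclusion.** The point holds as a minor gap in scope. For any within-series SD above zero, limits computed on averages are narrower than limits for one ARGOS-SC reading, and the plan neither labels them as limits for averages nor supplies the single-reading version.

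The direction is certain; the size is not established. Under the stated assumptions (s_avg 3.0 mmHg, σ_A 0.5–1.5 mmHg, three readings, normal differences, zero bias) the widening is about 1–8% and the 5 mmHg share loses 0.3 to 2.7 percentage points. If repeatability in the eye matched the bench specification, the widening would be about 1.6%. It would be larger if s_avg were smaller or σ_A larger than assumed.

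**What to change.** In SAP 8.5.1 and 11.2:

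- Keep the averages as the primary measures, and label the limits and the 5 mmHg share *for averages of 2–3 readings*.
- Add one row of limits for a single ARGOS-SC reading against mean GAT, and the same against mean DCT. Variance = variance of the difference of means + (1 − 1/m) × pooled within-series ARGOS-SC variance, with m the actual replicate count. For DCT, use the ARGOS-SC series taken after DCT.
- Use the pooled within-series variance. Squaring the mean of the SDs reported under 8.6.2 would understate it.
- Reconcile the SAP's 2–3 ARGOS-SC readings with the protocol's three, since m enters the formula.
- State that the corrected limits come from consecutive clinic readings and are a lower bound for home use.

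A row for one ARGOS-SC against one GAT reading is optional. If it is added, the formula is only approximate on the GAT side, because a third GAT reading is triggered by a difference of more than 2 mmHg.

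The cost is one formula and one table row per comparator, from readings already collected. The downside is that the quoted limits become slightly wider.
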